The study investigators will perform daily screening by chart review of patients admitted to the hospital in the previous 24 hours using the ICD-10 codes as below to find appropriate patients for secondary screening:

J13 Pneumonia due to Streptococcus pneumoniae

J14 Pneumonia due to Hemophilus influenzae

J15 Bacterial pneumonia, not elsewhere classified

J16 Pneumonia due to other infectious organisms, not elsewhere classified

J17 Pneumonia in diseases classified elsewhere

J18 Pneumonia, unspecified organism

J69 Pneumonitis due to inhalation of food and vomit

A partial HIPAA waiver will be obtained for the purposes of focused screening for eligibility. If the patient is deemed eligible for the study, the study investigators will approach the hospitalist/teaching attending for collateral information and permission to approach the patient for consent. After consent is obtained, the study investigator will perform a brief patient interview to obtain information on race/ethnicity, smoking and alcohol history, to confirm past medical and medication histories, and to perform baseline assessments of dyspnea (modified BORG).

Once consent is obtained, Patients will then be randomized using block randomization. We will receive pre-made envelopes in blocks of 10 from a centralized research coordinator. Investigators performing the initial screening and enrollment will be blinded to the envelope contents until after the patient consents to participation in the study. Once the patient consents to participation, the next consecutively numbered envelope will be opened revealing the allocation to either the control or intervention group. The principal investigator will keep the envelopes secured, and will be responsible for providing each envelope to the enrolling investigator after consent has been obtained.

The intervention will consist of oPEP therapy added to standard pneumonia care (see below). "Standard pneumonia care" will not be dictated by the study protocol, but rather at the discretion of the treating clinicians. Patients who are initially admitted to the intensive care unit (ICU) will not be included in this study even when they are downgraded to general medical floors, but patients will not be excluded if they are enrolled while on the medical floors and are later upgraded to ICU level of care. Enrollment will occur Monday through Friday, thus including patients being admitted on Sunday through Friday.

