Patients in the intervention group will be directed to perform the Aerobika therapy twice daily under the guidance of a study investigator for a total of at least 5 minutes per session. The study investigator will appropriately adjust the device on first use, as well as teaching the patient the correct technique for device usage. The primary patient-centered outcome will be the modified-Borg score for dyspnea which will be collected on admission, and on each subsequent morning until discharge on all enrolled patients. Patients will be encouraged to use the device on their own between the monitored sessions, as the device can safely be used multiple times daily. Patients will be surveyed each morning to self-report additional usage of the device. The device will also be available in the patient's room for in-line use of nebulizer treatments

administered by respiratory therapists, at the discretion of the therapist. Ordering of any nebulized medications is at the discretion of the treating clinicians or respiratory therapists, the latter through a standard and general respiratory therapist-driven protocol used in our institution. Charting of any nebulizer therapy will be reviewed to assess additional use of the device as well. The intervention will continue through the duration of the patient's hospitalization, and the patient will have the option to take the device at home with them if they wish to continue using it after discharge. If patients experience intolerable dyspnea or chest tightness during use of the Aerobika, despite coaching and troubleshooting by the bedside investigator, the Aerobika session will be aborted. If the patient is unable to tolerate the therapy during three consecutive sessions, then the patient will be withdrawn from intervention.

Crossover into the Aerobika group will not be restricted if the attending physician treating the patient deems it a necessary part of the patient's care. Rates of crossover will be collected as part of study data. All analyses will be performed using intention-to-treat as well as a modified intention-to-treat method considering the intervention group to include patients randomized to intervention AND who received at least one Aerobika treatment.

Variables to be collected

Demographics: Age at admission Gender Race/ethnicity (self-reported)	Lifestyle: Smoking history (ever/current/never) Alcohol consumption frequency

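### The protocol does not say who collects the daily modified Borg score or how, and nothing keeps the unmasked investigator who coaches the device from eliciting it

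*Combined protocol and SAP*

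**What the plan says.** All of this is in the combined protocol and SAP, mostly under Design.

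- **Coaching.** "Patients in the intervention group will be directed to perform the Aerobika therapy twice daily under the guidance of a study investigator". The investigator also sets up the device and teaches its use. No matching contact is described for controls.
- **Baseline score.** After consent, the study investigator interviews the patient and takes the baseline modified Borg. Randomization is described in the next paragraph.
- **Daily score.** The modified Borg "will be collected on admission, and on each subsequent morning until discharge on all enrolled patients". The sentence is passive. It does not say who collects the score, whether it is spoken or self-marked, or when it is taken relative to a device session.
- **Morning device survey.** "Patients will be surveyed each morning to self-report additional usage of the device". No surveyor is named.
- **Blinding.** The only provision is this: "Investigators performing the initial screening and enrollment will be blinded to the envelope contents until after the patient consents". After that, "the next consecutively numbered envelope will be opened revealing the allocation to either the control or intervention group". No sham, masked assessor, self-completion or collection script is described.
- **Status of the outcome.** Design states: "The primary patient-centered outcome will be the modified-Borg score for dyspnea". Objectives lists dyspnea first among the secondary outcomes, with length of stay as the primary outcome.

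**The concern.** The modified Borg is a rating that the patient gives, so the person asking and the manner of asking can move it. Here the study team knows the arm, spends time twice a day coaching one arm only, and has an interest in whether the device helps. If the investigator who coaches also asks for the morning score, a leading prompt, or a patient's wish to please the coach, could lower scores in the device arm more than in the control arm. Analysis cannot separate such a difference from a real effect, and the Statistical Analysis section offers nothing beyond an unspecified comparison of the groups.

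What is at stake is the credibility of any dyspnea finding. This is the outcome that speaks most directly to how patients feel.

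**Working it through.** **1. What is specified at each step**

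| Step | Who | How | Arm known? |
|---|---|---|---|
| Baseline Borg | Study investigator | Interview | Naturally read as before allocation, but not expressly required |
| Device sessions | Study investigator, device arm only | Coaching twice daily | Yes |
| Daily Borg, both arms | Not stated | Not stated | Not stated; no masking required |
| Morning survey of device use | Not stated | Not stated | Its content reveals the arm to whoever runs it |

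The gap is in the third row. The only method described for any Borg score is the investigator interview, and no text assigns the daily score to someone else or to the patient.

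**2. Order of baseline score and envelope**

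The text runs from consent to interview with baseline Borg, and then to randomization. The trigger written for the envelope, however, is consent: "Once the patient consents to participation, the next consecutively numbered envelope will be opened revealing the allocation". Recording the baseline score is never made a condition. The natural order is the right one, but it is not locked.

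**3. The plan's own figure**

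The documents give no figure for the Borg outcome. The number per arm comes from length of stay (Sample size calculations): means 4.6 and 3.45 days, difference 1.15, SD 3.16. Alpha and power are not stated; two-sided 0.05 and 80% are assumed.

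n = 2 × (1.960 + 0.842)² × 3.16² / 1.15² ≈ 118.5, rounded up to 119 per arm.

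This reproduces the stated 119 and supplies the n used below. It has no other bearing on the Borg question.

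**4. Hypothetical illustration of a shift in one arm**

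Assumptions, none of them in the documents: a Borg SD of 1.5 to 2.5; a shift of 0.25 or 0.5 points due to elicitation alone; zero true effect; one unadjusted two-sided 0.05 comparison with scores from all 119 patients per arm.

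z = shift / (SD × √(2/119)), with √(2/119) = 0.1296.

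P(significant) = 1 − Φ(1.960 − z) + Φ(−1.960 − z).

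Worked case, SD 2 and shift 0.5: z = 0.5 / (2 × 0.1296) = 1.928, so P = 0.487. For a shift of 0.25, z = 0.964 and P = 0.161.

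| SD | Shift 0.25 | Shift 0.5 |
|---|---|---|
| 1.5 | 25% | 73% |
| 2.0 | 16% | 49% |
| 2.5 | 12% | 34% |

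With no shift the chance is 5%. In SD units, a bias of 0.1 SD gives 12%, 0.2 SD gives 34% and 0.3 SD gives 64%. The table shows how sensitive the comparison is at this sample size. It does not show how large a shift is likely.

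**The case against.** Several stronger readings are tempting, and the documents do not support them.

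- **That coaching investigators do elicit the daily score face to face.** A reader might infer this from the coaching sentence and the baseline interview. The coaching sentence concerns device sessions, not dyspnea measurement, and the interview is documented for baseline only. For the daily score the protocol is silent. The silence is the defect; it is not evidence of a particular practice.
- **That the baseline is taken with the arm known.** The narrative puts the interview before randomization. The consent trigger leaves the order unenforced, but no procedure is described in which the envelope comes first.
- **That only device patients rate their breathlessness to the coaching team.** The score is collected on all enrolled patients, so controls may rate to the same people. The difference between arms lies in knowledge of the arm and in the amount of contact, not necessarily in who asks.
- **That the percentages estimate the bias.** They follow entirely from an assumed SD and an assumed shift. The protocol names no Borg time point or model, so even the form of the test is assumed.

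Two further objections stand in part. First, patients know whether they have the device, so expectation would bias the score whoever collects it, and the documents do not show what share is due to the interviewer. This limits the benefit of any change in collection but does not justify leaving the avoidable part unaddressed. Second, the primary outcome and the sample size rest on length of stay, and this point does not touch them. That is correct, and it limits the importance of the point.

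**Conclusion.** The point holds as a gap in specification. In a trial without masking, where investigators coach one arm only, the protocol sets no collector, method or script for the daily score of a subjective outcome. Nothing prevents the coaching investigator from eliciting it, so prompting that depends on arm could bias the dyspnea comparison. The baseline issue amounts to making explicit an order that the text already implies.

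The size is unknown. On the hypothetical inputs, a 0.5-point shift alone would raise the chance of a significant dyspnea difference from 5% to between 34% (SD 2.5) and 73% (SD 1.5). This rests on the assumed SD and shift, complete scores at 119 per arm, and a single unadjusted test.

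The consequence is confined to dyspnea: a listed secondary outcome, though Design gives it more prominence. Length of stay and its sample size are unaffected. This is a worthwhile low-cost improvement, not a threat to the trial's main conclusion.

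**What to change.** Two changes under Design:

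1. **Daily and baseline scores.** Have every patient in both arms mark the modified Borg personally on a printed or tablet scale, after one scripted instruction that is the same for everyone. The investigator does not read the scale out or show earlier scores.
2. **Randomization.** State that the envelope is opened only after the baseline score has been recorded.

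The cost is a printed card (or tablet form) and two protocol sentences. No additional assessor is needed, and neither treatment nor sample size changes. The downside is a few more blank or unclear scores. Patients will still know their arm, and device patients will still have more investigator contact, so the bias is reduced, not removed. Any report of the dyspnea result should say so.

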Home and inpatient medications: PPI/H2-blockers Statins? Hypoglycemics/insulin Systemic steroids Inhaled medications including by nebulization Immunosuppressives	Symptoms:

Physical/Vital signs: BMI (height/weight at admission) Heart rate (daily maximum/minimum) Pulse oximetry (daily maximum/minimum, including FiO2 maximum/minimum) Temperature (daily maximum/minimum) Blood pressure (daily maximum/minimum)	Comorbidities/Past Medical History : CVA Heart disease Renal failure Cancer, active in last 6 months or not (excluding non-melanoma skin cancers) Lung disease (ie. asthma, COPD, ILD, bronchiectasis) GERD Oropharyngeal or other dysphagia
Scores: PSI - pneumonia severity index CURB65 Subjective (cough, dyspnea, mucus production) Modified-Borg score for dyspnea	

Sample size calculations

The median hospital length of stay (LOS) for Norwalk Hospital based on FY2017 data was 4.6 days (SD 3.16 days) for patients coded with a primary diagnosis of pneumonia. We will employ an effect size of 25%, powering for a reduction in LOS by 1 day.

**Two independent study groups
The primary endpoint is an average LOS (continuous variable).**

Sample Size
 Group 1 119
 Group 2 119
 Total 238

Study Parameters
 Mean LOS, group 1 4.6
 Mean LOS, group 2 3.45

Patient identity will be protected through the use of the EHR, as well as by saving abstracted PHI on a password-protected, data-encrypted, secured drive managed by information

technology (IT) at Norwalk Hospital. Additional considerations include the use of REDCap, a secured research platform, for primary data collection and storage. Data will be destroyed when all analyses and publications have been completed.

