10. Pre-existing medical condition with a life expectancy of less than 3 months
11. Inability to form appropriate mouth seal on device (eg. due to neuromuscular disease)
12. Pre-existing active use of oPEP devices
13. Requiring $\geq 50\%$ FiO₂ or facemask (excluding high flow NC)

Assessment of Efficacy:

This study is not designed to assess the efficacy of any drug, supplement, device, etc.

Assessment of Safety:

No known safety issues exist as no procedures will be conducted on patients for this study outside of the scope of their current use. Furthermore all medical devices in this study are FDA approved and currently being used for the indication being studied in this project.

Statistical Analysis:

Comparative statistics will be employed to determine if outcomes in the intervention (oPEP) group are statistically different from those in the control group. This will be done with the assistance of in-network statisticians as well as available statistical software.

Direct Access to Source Data Documents:

The study's Principal Investigator, primary study coordinator, and co-investigators will have access to all study data. These data will be used for study purposes only, and will be stored on a password-protected, data-encrypted, secure drive managed by IT at Norwalk Hospital. Data may be released to regulatory agencies as necessary, including the US Food and Drug

Administration, Department of Health and Human Services agencies, BRANY, the WCHN IRB, accrediting agencies, and data safety monitoring boards.

References:

2. Diana Tydeman (1989) An investigation into the effectiveness of physiotherapy in the treatment of patients with community-acquired pneumonia, *Physiotherapy Practice*, 5:2, 75-81, DOI: 10.3109/09593988909044416

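### The FY2017 length of stay of 4.6 days is labelled a median but entered as the control-arm mean, and the target difference is given both as 25% (1.15 days) and as 1 day

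*Combined protocol and SAP*

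**What the plan says.** All the relevant statements are in the *Sample size calculations* section of the combined protocol and SAP.

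- Source of the baseline figure: "The median hospital length of stay (LOS) for Norwalk Hospital based on FY2017 data was 4.6 days (SD 3.16 days". It applies to admissions coded with pneumonia as the primary diagnosis.
- Target: "We will employ an effect size of 25%, powering for a reduction in LOS by 1 day".
- Endpoint: "The primary endpoint is an average LOS (continuous variable".
- Study parameters: "Mean LOS, group 1 4.6" and "Mean LOS, group 2 3.45", with 119 patients in each group and 238 in total.

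The section reports no separate FY2017 mean, and it states neither the significance level nor the power. *Statistical Analysis* does not fill the gap. It says only that "Comparative statistics will be employed to determine if outcomes in the intervention (oPEP) group are statistically different from those in the control group", without saying which summary of LOS will be compared.

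**The concern.** One number carries two names. The sentence on FY2017 data calls 4.6 days a median; the table, a few lines later, calls it a mean. The two coincide only if LOS is roughly symmetric, and the document's own figures make that doubtful. LOS cannot be negative, and the SD of 3.16 is 69% of 4.6, so zero lies only about 1.5 SD below the stated centre. Right skew, with the mean above the median, is the natural inference, although the document does not state it.

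What is at stake is the meaning of the planned effect on the primary outcome. If 4.6 is a median, then 4.6 and 3.45 are not mean stays, and 1.15 days is not 25% of the average on which the endpoint is defined. A reader of the results could not tell what percentage fall in mean LOS the trial was sized to detect.

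The sentence that sets the target has a second ambiguity, which needs no assumption about the distribution. It offers 25% and 1 day as the same thing, but 25% of 4.6 is 1.15 days.

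**Working it through.** **Inputs.** From *Sample size calculations*: baseline 4.6 days, SD 3.16, group means 4.6 and 3.45, 119 per group, 1:1 allocation. Not stated, and assumed here because they reproduce the plan's figure: two-sided alpha 0.05 and power 80%. The SD is taken as 3.16 in both groups throughout.

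**1. Reproduce the plan's figure.**
- 4.6 × 0.75 = 3.45, so the difference is 1.15 days, exactly 25% of 4.6.
- n per group = 2 × (1.960 + 0.8416)² × 3.16² / 1.15² = 118.5, rounded up to 119.
- Power at 119 per group is 80.2%.
- Other settings do not give 119 for this difference: one-sided 0.05 with 80% power gives 94, and two-sided 0.05 with 90% power gives 159.

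**2. Suppose 4.6 is the median.** The mean must then be inferred from a distributional shape with median 4.6 and SD 3.16. For a lognormal, write v = exp(σ²). Then v(v − 1) = (3.16/4.6)² = 0.472, so v = (1 + √(1 + 4 × 0.472))/2 = 1.350, and the mean is 4.6 × √1.350 = 5.34. The gamma (shape 2.73) and Weibull (shape 1.67) were solved numerically for the same median and SD.

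| Assumed shape | Mean (days) | 1.15 days as % of mean | 25% of mean (days) | n per group for 80% power | Power at 119 per group |
|---|---|---|---|---|---|
| Weibull | 5.12 | 22.5% | 1.28 | 96 | 87.8% |
| Gamma | 5.22 | 22.0% | 1.31 | 92 | 89.0% |
| Lognormal | 5.34 | 21.5% | 1.34 | 88 | 90.3% |

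The last three columns concern a true 25% fall in the mean. If the target stays at 1.15 days, n stays at 119, because the formula uses the difference and the SD and not the baseline level.

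**3. Suppose 4.6 is the mean.** The table, the 25% and the 119 all stand, and the sentence citing FY2017 data is mislabelled. The median would be lower: for a lognormal, 4.6 / √(1 + 0.472) = 3.8 days; for a gamma, about 3.9 days.

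**4. The 1-day wording.**
- 1 / 4.6 = 21.7%, not 25%.
- n per group for 1.0 day = 2 × (1.960 + 0.8416)² × 3.16² / 1.0² = 156.8, so 157 (314 in total).
- At 119 per group the standard error of the difference is 3.16 × √(2/119) = 0.410. Power for 1.0 day is Φ(1.0/0.410 − 1.960) = 68.5%.

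**The case against.** The best defence is that median is a slip of the pen. The figure is paired with an SD, the endpoint is called an average, and the table says mean. On that reading every number in the table stands and the repair is one word. This is plausible, and it may be the more likely explanation. It does not close the point, because the document gives no second figure to show which label is the slip; only the FY2017 data can. It is also possible in principle that mean and median are both 4.6, but with zero about 1.5 SD away that would need to be shown.

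It can also be said that the sample size is unharmed on either reading of 4.6. That stands in full.

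The 1-day phrase may be loose rounding of 1.15. That too is fair, but the rounding costs about 12 percentage points of power (80.2% against 68.5%), so the text should carry the figure actually used.

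Three stronger readings are tempting, and the document does not support them:

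- *The stated means and the 25% effect contradict each other.* They do not; 3.45 is exactly 75% of 4.6, and the pair reproduces 119.
- *Using a median as the mean leaves the trial too small.* Under right skew it works the other way: 25% of a higher mean is a larger difference, and at SD 3.16 the 119 per group is more than enough for it.
- *The primary comparison must therefore be rank-based.* A mislabelled planning figure does not decide the choice of test. That *Statistical Analysis* names no test is a separate matter.

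**Conclusion.** The point holds as a labelling and reporting defect in the planning of the primary outcome, not as an arithmetic error. Unless mean and median coincide, one of the two labels on 4.6 days is wrong.

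The effect is modest. If the table is mislabelled, the planned 1.15 days is about 21.5% to 22.5% of mean LOS instead of 25%, and 119 per group has about 88% to 90% power for a true 25% fall. If the sentence is mislabelled, one word changes. Neither case calls for a different sample size.

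The mismatch between 25% and 1 day is the part that bears on power, at about 68% for 1.0 day against about 80% for 1.15 days.

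These results rest on an inferred two-sided 0.05 and 80% power, and on a common SD of 3.16. The percentages also rest on an inferred right skew, with shapes chosen only to show the range.

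**What to change.** 1. Take the mean, median and SD of LOS from the same FY2017 extract, and label each one in the text.
2. Put the true mean in the table as the group 1 value and restate group 2 to match.
3. State the target on the scale of the endpoint, for example: 119 per group is sized for a 1.15-day difference in mean LOS, equal to x% of the FY2017 mean, at the alpha and power used. If the extract gives a different SD, rerun the formula with it.
4. In the same edit, replace the 1-day reduction with 1.15 days, or say that power for 1.0 day is only about 68%.

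Keep 119 per group. The cost is one query of data the hospital already holds and a few words in *Sample size calculations*, with no extra patients. The downside is that the quoted percentage or power may look slightly less favourable than the present text suggests.

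### The sample-size text claims power for a 1-day reduction in length of stay, but 119 per arm was sized for 1.15 days; power for 1 day is about 68% (two-sided 5%, inferred).

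*Combined protocol and SAP*

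**What the plan says.** Everything relevant is in the section Sample size calculations of the combined protocol and SAP.

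- The planning data: "The median hospital length of stay (LOS) for Norwalk Hospital based on FY2017 data was 4.6 days (SD 3.16 days").
- The target: "We will employ an effect size of 25%, powering for a reduction in LOS by 1 day".
- The endpoint: "The primary endpoint is an average LOS (continuous variable").
- The Study Parameters list: "Mean LOS, group 1 4.6" and "Mean LOS, group 2 3.45".
- The result: 119 per group, 238 in total.

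The available text gives no alpha, sidedness, power or dropout allowance. The Objectives name length of stay (LOS) as the primary outcome without giving a size of effect. The Statistical Analysis section says only that comparative statistics will be used to see whether outcomes "are statistically different from those in the control group". Neither section restates or corrects the target.

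**The concern.** The sentence that sets the target contains two sizes of effect, and they disagree. A 25% reduction from 4.6 days is 1.15 days; a 1-day reduction is 21.7%. The listed means follow the 25%, not the 1 day.

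The gap looks small in days, but the required sample size varies with the inverse square of the difference. Moving from 1.15 to 1.0 day multiplies it by 1.15² = 1.3225, an increase of about 32%. The error is also in the favourable direction: the plan claims sensitivity to a smaller effect than it was sized for. Anyone who takes the 1-day figure as the design target, for instance when interpreting a null result, would expect to miss such an effect about one time in five. The actual figure would be nearer one in three.

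**Working it through.** **Inputs from Sample size calculations.** Control mean 4.6 days; intervention mean 3.45 days; SD 3.16 days, taken as common to both arms; 119 per arm, 1:1; continuous endpoint, two independent groups.

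**Inputs inferred.** Two-sided alpha 5% and 80% power. Step 2 shows why. No weight is placed on their absence from the text.

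**Step 1: the two targets.**

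- 4.6 × 0.75 = 3.45, and 4.6 − 3.45 = 1.15 days, which is 25%.
- 1 / 4.6 = 21.7%.

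**Step 2: reproduce the planned number.** The normal approximation is

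n per arm = 2 (z₁₋α/₂ + z₁₋β)² SD² / d²

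With z values 1.960 and 0.842:

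- d = 1.15: 2 (1.960 + 0.842)² × 3.16² / 1.15² = 118.5, rounded up to **119**. This is the plan's figure.
- d = 1.0: 2 (1.960 + 0.842)² × 3.16² / 1.0² = 156.8, rounded up to **157**.

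The t-test versions are 119.5 (120) and 157.7 (158).

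**Step 3: could other settings give 119 for 1.0 day?** The grid covered alpha of 1%, 2.5%, 5% and 10%, one- and two-sided, with power from 70% to 95% in 5-point steps.

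- For d = 1.0, no combination gives 119. The nearest are 123.3 (two-sided 5%, 70% power) and 123.5 (one-sided 5%, 80% power), both 124 after rounding up.
- For d = 1.15, 119 appears only at two-sided 5% (equivalently one-sided 2.5%) with 80% power.
- At two-sided 5% and 80% power, 119 would fit 1.0 day only if the SD were about 3.16 / 1.15 = 2.75. The plan states 3.16.

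**Step 4: power at 119 per arm, two-sided 5%.** The standard error of the difference is 3.16 × √(2/119) = 0.410, and power = Φ(d / SE − 1.960).

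| True difference | Power, normal | Power, t-test | n per arm for 80% power (normal / t-test) |
|---|---|---|---|
| 1.15 days | 80.2% | 79.8% | 119 / 120 |
| 1.0 day | 68.5% | 68.1% | 157 / 158 |

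The loss is 80.2 − 68.5 = 11.7 points (normal) and 79.8 − 68.1 = 11.7 points (t-test).

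**Step 5: smallest difference detectable with 80% power at 119 per arm.** (1.960 + 0.842) × 0.410 = 1.148 days (normal); the t-test gives 1.152. Both round to 1.15 days.

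**The case against.** The best defence is that 1 day is loose rounding. The same sentence says 25%, the list below it gives 3.45, and the sample size agrees with both. Only the whole-day gloss differs, so nothing in the calculation is wrong and a careful reader can recover the true target. This is probably how the sentence arose, and it means the sample size itself is not in question. It does not rescue the sentence, because the wording attaches the claim of power to the 1-day figure and that rounding is worth about 12 points of power.

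The second objection is that 68% depends on an alpha the text does not state. That is true. With a one-sided 5% test, power for 1.0 day at 119 per arm would be 78.7%. But at 80% power that test needs 94 per arm for 1.15 days or 124 for 1.0 day, not 119, whereas two-sided 5% gives 119 exactly. The non-directional wording in Statistical Analysis also fits a two-sided test. The grid is not proof by itself, since a power value between its steps can match any sample size. For 1.0 day at two-sided 5%, that value is the 68.5% above. The mismatch between 1 day and 1.15 days needs no alpha at all.

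A third point stands. The plan calls 4.6 a median and then lists it as a mean. If the true mean differs, 1.15 days is not 25% of it. This does not affect the power figures, which use the difference in days and the SD, but the corrected text should say so.

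**Conclusion.** The concern holds. The plan says it is powered for 1 day, while its percentage, its listed means and its sample size all correspond to 1.15 days. At 119 per arm, power for a true 1.0-day difference is about 68%, some 12 points below the figure for 1.15 days.

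The inconsistency between the two targets is certain from the text. The 68% rests on a common SD of 3.16, no dropout, and a two-sided 5% test, the last inferred from the exact reproduction of 119. It is not shown that the trial is underpowered for its intended target: if 1.15 days was intended, the size is correct and only the wording is wrong. It should be fixed because it misstates the design target for the primary endpoint.

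**What to change.** Keep 238 patients and replace the 1-day clause with wording such as:

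> With 119 patients per arm, the trial has about 80% power (two-sided 5%) to detect a 1.15-day difference in mean LOS, assuming an SD of 3.16 days. The 1.15 days is 25% of 4.6 days, the FY2017 median, used here in place of the mean. Power for a 1.0-day difference is about 68%.

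The sponsor should confirm the alpha, sidedness and power actually used before this text is adopted. The cost is a wording change, with no extra patients and no change to conduct or analysis.

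If 1 day is the difference the sponsor really wants to detect, the plan should say openly that 238 patients give about 68% power for it. Restoring 80% would take 157 to 158 per arm, or 314 to 316 in total, which is 76 to 78 more than planned. The listed parameters do not point to that reading, so the wording change is the recommended course.
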